8. REGULATORY ISSUES.....	9
8.1 ETHICS APPROVAL	9
8.2 CONSENT.....	10
8.3 CONFIDENTIALITY	10
8.4 INDEMNITY	10
8.5 SPONSOR	10
8.6 FUNDING.....	10
8.7 AUDITS	10
9. STUDY MANAGEMENT.....	10
10. PUBLICATION POLICY	11
11. REFERENCES	11
Kessels, R. (2003). Patients' memory for medical information. JRSM, 96(5), pp.219-222.	11

GLOSSARY OF ABBREVIATIONS

STUDY SUMMARY

TITLE	Optimising Consultation Summaries to Promote Good Health; Views of Adolescents Attending Diabetes Clinic
DESIGN	Qualitative study involving interviews with young adults face to face and over the phone
AIMS	What are young people's beliefs about the role of consultation summaries and how they can be improved to promote good health
OBJECTIVES	To understand whether consultation letters are being read by the young people To explore their opinions about consultation letter contents and their impact To explore young people's ideas for optimising these letters
POPULATION	12-18 young people aged 12-18 who have been visiting UCLH adolescent diabetes outpatient clinic chosen using purposive sampling
ELIGIBILITY	Adolescents aged 12-18 years attending a diabetes outpatient clinic
DURATION	16 Months. April 2018 – August 2019

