1. INTRODUCTION

1.1 BACKGROUND

Patient participation in decision making process about their care promotes patient satisfaction and confidence (Harris and Boaden, 2006). As part of this, allowing patients to see letters written about them enables trust, encourages patients to be involved in decision making process and allow patient understanding (Baxter et al., 2008). Given all above, the 2000 NHS plan made it a requirement that all medical correspondence between health professionals is shared with patients (Department of Health, 2004).

It is estimated that 40-80% of information discussed during a consultation is forgotten immediately (Kessels, 2003). Given this, written summaries have shown to be an effective method of improving patient recall of information by 20.8% (Chan et al., 2002).

The literature on the benefits/disadvantages of consultation summaries is largely focused on adult patients with little research done to explore the views of adolescent population. Where the patient is a child, the literature is only focussed on parents of children and not the children themselves. Limited research has shown that parents/care givers report clinic letters being useful in assisting with better understanding and management of their child's condition (Lawton et al., 2015; Waterston and Lazaro, 1994).

It is not known if young people value consultation summaries in the same way. Only one study focused on adolescent views reports young people wishing to receive summaries about themselves and finding them useful (Bartle et al., 2004).

Adolescence is an important time of an individual's life. This is the time when many independent health behaviours are established. During adolescence, young people start showing more interest in their own health and often wish to participate in decision making processes regarding their care. The role of health workers at this stage is to appreciate young people as individuals (Viner and Macfarlane, 2005). Clinic summaries addressed directly to young people might play an important role in assisting with establishment of health behaviours and promoting good health in young people.

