1.2 RATIONALE FOR CURRENT STUDY

The aim of this research is to understand the views of adolescent patients on consultation summaries and identify factors can improve these summaries and subsequently their health and well-being.

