2. STUDY OBJECTIVES

1. To understand whether consultation letters are being read by the young people
2. To explore their opinions about consultation letter contents and their impact
3. To explore young people's ideas for optimising these letters

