Interviews will be conducted by a researcher experienced in qualitative studies. The discussion will be held in a quiet room with refreshments provided. Phone interviews will also be conducted in a quiet room with one researcher in the room communicating with a participant. The discussion will take no longer than 30 minutes. Parents will be asked to remain in the waiting area during the study as per NCB Guidelines (NCB Guidelines for Research with Children and Young Adults, 2011).

The researcher will voice a series of prepared statements/questions to promote interview (appendix 1). Written assent/consent will be obtained from study participants and their parents (if present) at the beginning of the discussion or in clinic if phone interview is preferred. The discussion will be audio-recorded.

Audio-recordings from each discussion will be transcribed by [name]. The transcripts will be immediately anonymised. Data analysis will involve a general thematic coding method and will be analysed by two independent researchers (Flick 2009).

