7. DATA ANALYSIS

We will use constant comparative method for the coding process (Krueger and Casey, 2015). The coding process will consist of reading the transcript and analysing responses to statements given by the study participants one by one. We will examine responses to each statement and code each response according to what it describes. If there are several responses to the same statement given, these will be analysed for similarity. If similar, the same code will be given to each, if different, different codes will be given. This coding approach will be maintained for all responses.

In order to avoid analysis errors, transcripts will be coded by two researchers ([name] and [name]) independently and differences agreed. Once the coding process is complete, we will categorize codes and analyse them for frequency, extensiveness, intensity, specificity, internal consistency and participant perception of importance (Krueger and Casey, 2015).

We will share the study outcomes with all participants and their families. We will submit the findings in a peer-reviewed medical journal.

Data and all appropriate documentation will be stored for a minimum of 10 years after the completion of the study, including the follow-up period.

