Appendix 1 – Focus group discussion schedule

Tell us a bit about the letters you get

1. Is the letter directed to you, your parent/carer, GP or another doctor?
2. Who reads the letter, you or your parent/carer?
3. Do you show consultation letters to?

Letter content

4. Is the language easy to understand (eg medical terms) What could be better?
5. Does the letter sound friendly or professional to you? How could it be better?
6. Is it too long/short? How could it be better?
7. Does it talk about the right things? How could it be better?

Do these letters help you to improve your health?

8. Are they helpful in any way? (motivate, remind, congratulate, give ideas)
9. Are they unhelpful in any way? (remind of negatives, demoralise, feel sad/worried/angry)
10. What else about your letters could help? Other ideas?

Potential areas of improvement

1. Is there anything that can be improved?
2. Is getting them by post ok? (email/text/postcards better?)

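### The aim is young people's beliefs about the role of consultation letters, but the interview schedule has no open question on what the letters are for

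*Protocol*

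**What the plan says.** The Study Summary puts the research question as young people's "beliefs about the role of consultation summaries and how they can be improved to promote good health". Section 1.2 words the aim more broadly, as to "understand the views of adolescent patients on consultation summaries and identify factors can improve these summaries". Section 2 turns it into three objectives: whether the letters are read, opinions on content and impact, and ideas for improvement. The second reads "To explore their opinions about consultation letter contents and their impact". None of the three uses the word role.

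Appendix 1 is the instrument. Section 6 says: "The researcher will voice a series of prepared statements/questions to promote interview (appendix 1"). The same section limits the discussion to 30 minutes, interviews each participant once, and plans for 12-18 interviews or until themes saturate. Section 7 describes the coding: "We will examine responses to each statement and code each response according to what it describes".

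The item closest to role is item 8: "Are they helpful in any way? (motivate, remind, congratulate, give ideas"). It stands with items 9 and 10 under a heading that itself asks about benefit to health.

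**The concern.** Beliefs about role are the first thing the aim names. To learn what someone believes a letter is for, the usual course is to ask openly before offering any candidate answers. Appendix 1 does not do this. Item 8 asks whether the letters help, which is a different question, and it names four functions chosen by the investigators.

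Two young people can hold quite different beliefs and give the same answer. One may see the letter as a record for the GP, the other as a personal plan, and both can say that it reminds them. The schedule gives no planned opportunity to tell these beliefs apart. If the bracketed words are read out, the functions that come up most often will partly reflect the list. Section 7 intends to analyse codes for frequency, among other properties, and there would be no planned unprompted answer to compare with.

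**Working it through.** No arithmetic beyond a count applies, because the study is qualitative and this point rests on no stated figure. The check sets the 12 numbered items of Appendix 1 (3 + 4 + 3 + 2 = 12) and its headings against the aim and objectives.

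| Part of the aim or objectives | Where Appendix 1 reaches it | Form of the question |
|---|---|---|
| Aim, first half: beliefs about role | No item directly; approached by item 8 and the heading above items 8-10 | Closed; item 8 lists four functions |
| Aim, second half, and Objective 3: improvement | Follow-ups in items 4-7, item 10, both closing items | Largely open |
| Objective 1: are letters read | Item 2, with items 1 and 3 as context | Factual |
| Objective 2: contents | Items 4-7 | Closed stem with an open follow-up |
| Objective 2: impact | The heading, item 8 (helpful effects), item 9 (unhelpful effects) | Closed and prompted; item 10 is open but asks what else could help |

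The counts are:
- Items asking what the letters are for, or why they are sent: 0 of 12.
- Items asking about perceived good or bad effects: 2 of 12 (items 8 and 9), under one heading that is itself a direct question on health.
- Items asking what the young person did about their health after a letter: 0 of 12. Item 3 concerns only showing the letter to others, and as printed the sentence is incomplete.

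Next, can later stages make up for the missing question?
1. Coding in Section 7 starts from responses to each prepared statement. A question that is not asked has no set of responses of its own.
2. Each participant is interviewed once, so there is no planned second occasion to ask.
3. Recruitment may stop at theme saturation. If role is not raised systematically, saturation on the other topics says little about saturation on role.
4. No written probe on purpose appears in Section 6 or Appendix 1, so raising it depends on the interviewer or the participant.

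The protocol does not say whether the bracketed words in item 8 are read out or kept in reserve. If they are read out, the answers are prompted from the start. If they are kept back, the item still asks about helpfulness and not about purpose.

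**The case against.** The other side has a good deal in its favour.

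- **Role can be read functionally.** Section 1.1 uses the word that way when it says letters addressed to young people "might play an important role in assisting with establishment of health behaviours and promoting good health in young people". On that reading the health heading and the item 8 functions do address role. This stands in part: role is approached, but through a list supplied by the investigators.
- **The objectives operationalise the aim.** Section 1.2 speaks only of views, and leaving out one word between aim and objectives is not a contradiction. That is fair. Even so, the Study Summary states the aim in terms of role, and the instrument should serve it.
- **This is a guide for an experienced interviewer, not a fixed questionnaire.** Remarks on purpose can arise unprompted and would be coded by what they describe. Items 1-3 also give context on who receives, reads and sees the letter. This reduces the gap but does not close it, since addressee and reader are not beliefs about purpose.

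Three stronger readings are tempting, and the protocol does not support them. A reader might infer that impact on health has to be deduced from items 8 and 9 alone. In fact the heading asks about it directly, item 9 invites harms, and item 10 is open. A reader might infer that the study cannot report beliefs about role at all. That is too absolute, for the reasons just given. A reader might also treat the lack of a question on behaviour after a letter as an error. Objective 2 promises opinions on impact, not accounts of behaviour, and Section 1.1 says only that letters might play a part in health behaviours.

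**Conclusion.** The point holds in a limited form and is minor. The first half of the aim in the Study Summary has no open question in Appendix 1 (0 of 12 items) and is reached only through one prompted item and one closed heading. Perceived impact is asked about directly, but in closed and prompted wording. The consequence is weaker, partly led evidence on beliefs about role; the study can still proceed and report. The conclusion assumes that interviewers broadly follow the schedule as written and that no separate guide with further probes exists. If interviewers routinely ask about purpose, the gap is smaller still, and writing the question down would only make it consistent across the 12-18 interviews.

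**What to change.** In Appendix 1, after item 3 and before the items on content, add one open question: *What do you think these letters are for?* In Section 7, state that the answers will be coded as beliefs about role, separately from answers given to the item 8 prompts. Functions volunteered can then be distinguished from functions recognised in a list.

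As an optional follow-up to items 8 and 9, ask for an example of a time a letter did or did not make a difference. This would give substance to yes/no answers, but the objectives do not require it.

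The cost is a few minutes of the 30-minute interview. That is an assumption, as the protocol gives no timing per item. It can be offset by dropping the first item under the closing section on improvement, which largely repeats item 10. Section 8.1 records that ethics approval is already held, so the change may need to be notified to the committee. The alternative is to bring the aim in the Study Summary into line with Section 1.2, so that the study claims only general views; this needs no new question but gives up part of the stated question.

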1. INTRODUCTION

1.1 BACKGROUND

Patient participation in decision making process about their care promotes patient satisfaction and confidence (Harris and Boaden, 2006). As part of this, allowing patients to see letters written about them enables trust, encourages patients to be involved in decision making process and allow patient understanding (Baxter et al., 2008). Given all above, the 2000 NHS plan made it a requirement that all medical correspondence between health professionals is shared with patients (Department of Health, 2004).

It is estimated that 40-80% of information discussed during a consultation is forgotten immediately (Kessels, 2003). Given this, written summaries have shown to be an effective method of improving patient recall of information by 20.8% (Chan et al., 2002).

The literature on the benefits/disadvantages of consultation summaries is largely focused on adult patients with little research done to explore the views of adolescent population. Where the patient is a child, the literature is only focussed on parents of children and not the children themselves. Limited research has shown that parents/care givers report clinic letters being useful in assisting with better understanding and management of their child's condition (Lawton et al., 2015; Waterston and Lazaro, 1994).

It is not known if young people value consultation summaries in the same way. Only one study focused on adolescent views reports young people wishing to receive summaries about themselves and finding them useful (Bartle et al., 2004).

Adolescence is an important time of an individual's life. This is the time when many independent health behaviours are established. During adolescence, young people start showing more interest in their own health and often wish to participate in decision making processes regarding their care. The role of health workers at this stage is to appreciate young people as individuals (Viner and Macfarlane, 2005). Clinic summaries addressed directly to young people might play an important role in assisting with establishment of health behaviours and promoting good health in young people.

1.2 RATIONALE FOR CURRENT STUDY

The aim of this research is to understand the views of adolescent patients on consultation summaries and identify factors can improve these summaries and subsequently their health and well-being.

2. STUDY OBJECTIVES

1. To understand whether consultation letters are being read by the young people
2. To explore their opinions about consultation letter contents and their impact
3. To explore young people's ideas for optimising these letters

3. STUDY DESIGN

We are using patients attending a specialist diabetes clinic as our cohort and conducting a qualitative study involving individual interviews in clinic or over the phone.

Duration of the study is 16 months, April 2018 – August 2019.

Study population is 12-18 young people aged 12-18 who have been visiting UCLH adolescent diabetes outpatient clinic chosen using purposive sampling.

4. PARTICIPANT ENTRY

4.1 PRE-REGISTRATION EVALUATIONS

We will recruit patients from a single diabetes clinic serving patients from a very wide geographic area with wide socio-economic backgrounds. We will recruit and interview **between August 2018 – April 2019**.

4.2 INCLUSION CRITERIA

Adolescents aged 12-18 years attending a diabetes outpatient clinic

4.3 EXCLUSION CRITERIA

Young people who cannot speak English (effective communication with colleagues during the study is the major aspect for valid data collection)

Young people who refuse to participate in individual interviews

4.4 WITHDRAWAL CRITERIA

Participant's wish to voluntarily withdraw from the study

5. ADVERSE EVENTS

5.1 DEFINITIONS

Adverse Event (AE): any untoward medical occurrence in a patient or clinical study subject.

Serious Adverse Event (SAE): any untoward and unexpected medical occurrence or effect that:

- **Results in death**
- **Is life-threatening** – refers to an event in which the subject was at risk of death at the time of the event; it does not refer to an event which hypothetically might have caused death if it were more severe
- **Requires hospitalisation, or prolongation of existing inpatients' hospitalisation**
- **Results in persistent or significant disability or incapacity**
- **Is a congenital anomaly or birth defect**

Medical judgement should be exercised in deciding whether an AE is serious in other situations. Important AEs that are not immediately life-threatening or do not result in death or hospitalisation but may jeopardise the subject or may require intervention to prevent one of the other outcomes listed in the definition above, should also be considered serious.

5.3 REPORTING PROCEDURES

All adverse events should be reported. Depending on the nature of the event the reporting procedures below should be followed. Any questions concerning adverse event reporting should be directed to the Chief Investigator in the first instance.

5.3.1 Non serious AEs

All such events, whether expected or not, should be recorded.

5.3.2 Serious AEs

An SAE form should be completed and faxed to the Chief Investigator within 24 hours. However, **relapse and death due to <condition>**, and hospitalisations for elective treatment of a pre-existing condition do not need reporting as SAEs.

All SAEs should be reported to the **<name of REC>** where in the opinion of the Chief Investigator, the event was:

- 'related', ie resulted from the administration of any of the research procedures; and
- 'unexpected', ie an event that is not listed in the protocol as an expected occurrence

Reports of related and unexpected SAEs should be submitted within 15 days of the Chief Investigator becoming aware of the event, using the NRES SAE form for non-IMP studies. The Chief Investigator must also notify the Sponsor of all SAEs.

Local investigators should report any SAEs as required by their Local Research Ethics Committee, Sponsor and/or Research & Development Office.

Contact details for reporting SAEs
[contact]
CI email [contact]
Attention [name]
Please send SAE forms to: REC
Tel: **xxx** (Mon to Fri 09.00 – 17.00)

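### Does the unfilled template field in the SAE-reporting exemption (Protocol 5.3.2) call for a change to the plan?

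*Protocol*

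**What the plan says.** Section 5.1 of the Protocol defines an SAE as "any untoward and unexpected medical occurrence or effect that" meets one of five listed criteria, of which one is "Results in death". Section 5.3 opens with "All adverse events should be reported". It goes on to say that the procedure to follow depends on the nature of the event and is set out in the subsections beneath it, and adds: "Any questions concerning adverse event reporting should be directed to the Chief Investigator in the first instance".

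Section 5.3.2 gives the procedure for serious events: "An SAE form should be completed and faxed to the Chief Investigator within 24 hours". Its next sentence carves out two groups, "relapse and death due to <condition>" and elective admissions, in the words "hospitalisations for elective treatment of a pre-existing condition do not need reporting as SAEs". The same section sends to the ethics committee, within 15 days, those SAEs that are unexpected and also related, meaning that the event "resulted from the administration of any of the research procedures". It separately requires the Chief Investigator to tell the Sponsor of all SAEs, and local investigators to report as their own bodies require.

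**The concern.** The angle-bracket field is template text that nobody completed. It is not a redaction: personal data removed from the document appear in square brackets, and section 5.3.2 contains a second unfilled angle-bracket field where the ethics committee's name should stand. No other section says which condition is meant, and relapse occurs nowhere else.

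The blank sits in an exemption, and the exemption concerns deaths. One member of staff could conclude that nothing is exempt, because no condition is named. Another could insert diabetes, the only condition in the inclusion criterion (section 4.2), and conclude that a death from the disease for which every participant attends the clinic needs no 24-hour form. The two answers are opposite, in a study that enrols from age 12. At stake would be prompt notice of a death to the Chief Investigator. The exemption also appears to cut across the definition in section 5.1 and the general reporting rule in section 5.3.

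**Working it through.** No figure is involved, so the check sets the sections side by side.

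1. **Is the blank real?** Yes. Nothing in the Protocol supplies the condition. The neighbouring blank for the ethics committee can be resolved, because section 8.1 names the committee. The blank for the condition cannot.

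2. **Does section 5.3.2 contradict section 5.1?** No. Section 5.1 says what counts as serious; section 5.3.2 says what is reported, to whom and how fast. An exemption from reporting does not alter a definition. The elective-admission exemption shows this: section 5.1 lists hospitalisation without qualification, section 5.3.2 exempts one kind of it, and the two can be read together without difficulty. The death clause has the same structure. What it lacks is its object.

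3. **Does section 5.3.2 contradict section 5.3?** No. The sentence after the general rule in section 5.3 defers to the procedures that follow, so section 5.3.2 applies that rule by event type.

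4. **Which reporting routes does the blank touch?**
   - The 24-hour form to the Chief Investigator is directly in doubt for a death from the unnamed condition.
   - The Sponsor notice covers all SAEs. Such a death is still an SAE under section 5.1, so on a literal reading the notice still applies. A reader who takes the exemption broadly might think otherwise.
   - The local-investigator reports follow the same logic.
   - The ethics committee route requires that the event arose from a research procedure. Here the procedure is an interview, so a death from an underlying disease would hardly enter this route under any reading of the blank.

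5. **How much exposure is there?** Section 3 describes a qualitative interview study with 12 to 18 participants and no study treatment. Section 6 says each is interviewed once, for no longer than 30 minutes. The Protocol gives no expected number of deaths, so no event count can be derived.

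6. **Does any result depend on it?** The objectives in section 2 and the coding and thematic analysis in sections 6 and 7 use transcripts only. No safety endpoint or event rate is analysed, and no stopping rule is tied to adverse events. Whichever way the blank is read, the data analysed and the conclusions are the same.

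Two neighbouring points add nothing. The contact block at the end of section 5.3.2 has a line sending SAE forms to the ethics committee, but other lines of that block were removed before publication, and the body text states both routes plainly. The word unexpected appears both in the SAE definition and in the ethics committee filter. The Protocol lists no expected occurrences, so the filter currently excludes no event.

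**The case for a change.** The strongest argument for acting is that SAE reporting is an operative rule and not a detail to be left to an analysis plan. An exemption for deaths that nobody can interpret should not remain in an approved protocol, however rarely it would be used. Referring questions to the Chief Investigator helps only those who notice the gap and ask. The correction would cost one clause.

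Much of this stands. The field is unfilled, its scope cannot be recovered from the document, and the cost of tidying is trivial. What does not follow is that the plan needs changing. The argument shows that a sentence is incomplete. It does not show that an event would go unnoticed, that a participant would be exposed to a risk created by the study, or that any finding would differ. The reading that exempts diabetes deaths requires a reader to supply a word that the Protocol does not contain. A reader who stays with the text has no named condition on which to base an exemption, and has a stated contact for questions. The participants' age explains why care in drafting is desirable, but it does not widen what the blank affects.

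**Conclusion.** The unfilled field in section 5.3.2 is a clerical slip left over from a template. Its reach is narrow: the 24-hour form, for a death from an unnamed condition, among 12 to 18 people each interviewed once without any study treatment. Sections 5.1, 5.3 and 5.3.2 do not otherwise conflict on this point, the other reporting duties stand as written, and no result or conclusion depends on the clause.

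This rests on two assumptions: that the study is conducted as described, with the interview as the research procedure, and that staff in doubt use the route to the Chief Investigator given in section 5.3. The sponsor can complete or strike the leftover words, and enter the committee named in section 8.1, whenever the document is next edited. Which events, if any, should be exempt is for the sponsor to settle and is not a statistical matter. No change to the plan follows.
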